1 SYNOPSIS

Clinical Investigation Title	Pediatric Performance and Satisfaction of Oticon Medical Ponto on Softband
Investigation Code	BC117
Investigational Device (s)	Oticon Medical Ponto sound processor on Ponto Softband solution
Principal investigator(s):	N/A – online survey, Oticon Medical, LLC
Sponsor:	Oticon Medical AB [name]
Objective(s):	Primary Objective 
• Evaluate subjectively hearing performance of Oticon Medical Ponto sound processors on Ponto Softband• Evaluate subjectively overall satisfaction of Oticon Medical Ponto sound processors on Ponto Softband
Methodology:	Observational survey study
Inclusion/exclusion criteria:	1. Consent provided 2. Parent or primary caregiver of child (< 18 years) currently using a Ponto Softband for Ponto Sound Processor
Endpoints	Primary Endpoints 
• Overall PEACH scores• Overall GCBI scores• Outcomes of satisfaction questionnaire
Duration of study period:	24 months or when targeted number of participants (40) have been enrolled.
Number of participants targeted:	40
Investigation plan prepared by:	[name], Clinical Project Manager, Oticon Medical, LLC [name], Clinical Research Manager, Oticon Medical, LLC

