5.3 Population and indications

The study population of interest is children below the age of 18 who are currently wearing a softband coupled to a Ponto sound processor. Parents or primary caregivers will be the surveyed population.

The softband solution is intended for children with conductive/mixed hearing loss and single-sided deafness who cannot be fitted or are waiting to be fitted with a surgically placed bone anchored hearing implant. It can often be recommended for individuals who do not benefit from conventional hearing aids who have ear problems such as blockages or infections, who present with a high likelihood of implant extrusions or skin care related burdens or who have thin or irregular skull bone (i.e. syndromic children).

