8.1 Primary objective

Primary objective	Corresponding primary endpoint/outcome variable(s)	Section
A. To investigate hearing performance of children wearing Oticon Medical Ponto sound processors on Softband	PEACH questionnaire evaluating Aural/Oral performance of children in quiet, noise and overall.	9.2.1
B. To investigate overall satisfaction of Oticon Medical Ponto sound processors on Softband	GCBI questionnaire evaluating health related benefit after hearing intervention for children. By answering specialized questionnaire to gather feedback on wear and general comfort of the Oticon Medical Softband.	

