9 DESIGN OF THE CLINICAL INVESTIGATION

9.1 Subject population

The population for this study will be children who use a Ponto Sound Processors on a Ponto Softband in the United States. Parents or caregivers of users (hereforth referred for as “participants” who are part of Oticon Medical’s US user database, who signed up for inclusion in the database when fitted with a Ponto Sound Processor will be approached through email out-reach. When signing up for the database participants give their consent to be contacted by Oticon Medical. In all cases, study awareness and enrollment in this study will occur only after being fitted with Ponto sound processor(s) on a softband solution.

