9.1.1 Inclusion criteria

The following participants will be included in the study:

	Title BC117 - Pediatric Performance and Satisfaction of Oticon Medical Ponto on Softband	Document no Doc-00121767	Revision 0	Page 8(17)
---	--	------------------------------------	----------------------	----------------------

- Individuals who are a parent or guardian of a softband user who are at or above the age of majority (AOM). AOM is 21 in Mississippi, 19 in Nebraska and Alabama, and 18 in all other US states.
- Participants provided study-specific consent before completing the survey.
- Users fitted with at least one Ponto Sound Processor on a softband at the time of the survey.

9.1.2 *Exclusion criteria*

The following participants will be excluded from the study:

- Participants who did not provide consent or later revoked consent.
- Under the AOM

9.1.3 *Number of Subjects*

The aim is to enroll 40 participants within 24 months.

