after a healthcare intervention. The GCBI is a parent-completed questionnaire comprised of 24 questions that query various aspects of a child's daily life and is worded to apply to children of any age. The GCBI is commonly modified to be used in any area of paediatric medicine. For this study, "operation" will be adapted to "Ponto sound processor on Softband", (Appendix B).

Softband specific questionnaire

The softband-specific questionnaire was developed by Oticon Medical and consists of questions designed to be completed by parents or other caregivers of children who are currently fitted with a Ponto sound processor on a softband.

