11 STATISTICAL DESIGN AND ANALYSIS

The results of the questionnaires will be analyzed and presented using descriptive statistics including the mean, standard deviation, median, and range.

The sample size in the investigation is not hypothesis-driven, but rather based on the number of users in the database which fit the inclusion criteria as well as estimations derived from previous survey study response rates from social media and other Oticon Medical reach out efforts.

No imputations or estimations will be made to replace missing data.

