Ponto 5 SuperPower

I don't know / other model

10. Think about how much your child used their sound processor(s) over the past two weeks. On an average day, how many hours did they use the sound processor(s)?

none
less than 1 hour a day
1 to 4 hours a day
4 to 8 hours a day
more than 8 hours a day

**11. Think about a situation where your child wanted to hear better, before receiving their sound processor.
Over the past two weeks, how much has the sound processor(s) helped in that situation?**

helped not at all
helped slightly
helped moderately
helped quite a lot
helped very much

12. How satisfied overall are you with your child's Ponto experience?

very much
quite a lot
moderately
slightly
not at all

13. How satisfied overall are you with your child's softband?

very much
quite a lot
moderately
slightly
not at all

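### Does the plan leave open whether a child who is fitted with the device but not wearing it counts in the PEACH summary?

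*Combined protocol and SAP*

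**What the plan says.** The combined protocol and SAP describes the child in several ways.

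- The Synopsis criterion is "Parent or primary caregiver of child (< 18 years) currently using a Ponto Softband for Ponto Sound Processor".
- Section 5.3 gives the population of interest as "children below the age of 18 who are currently wearing a softband coupled to a Ponto sound processor".
- Objective A in 8.1, whose endpoint is PEACH, reads "To investigate hearing performance of children wearing Oticon Medical Ponto sound processors on Softband".
- Section 9.1 opens by defining the population as children who use the processor on the softband. It later says that "enrollment in this study will occur only after being fitted with Ponto sound processor(s) on a softband solution".
- Section 9.1.1 asks in its first bullet for the parent or guardian of a softband user, and in its third for "Users fitted with at least one Ponto Sound Processor on a softband at the time of the survey".
- Section 9.2.1 says that the softband questionnaire is for caregivers of "children who are currently fitted with a Ponto sound processor on a softband".

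Appendix C asks about current use (item 1, yes or no) and average daily hours over the past two weeks (item 10, first option: none). PEACH item 1 in Appendix A scores wear from 0 (never) to 4 (always). On analysis, Section 11 says: "The results of the questionnaires will be analyzed and presented using descriptive statistics including the mean, standard deviation, median, and range". It adds that missing data will not be imputed. It defines no analysis set and ties no consequence to a No on item 1 or a none on item 10.

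**The concern.** Being fitted and wearing are different things for a child who owns the device but leaves it in a drawer. Read alone, the third bullet of 9.1.1 lets that child in, while 5.3 and Objective A seem to leave the child out. The survey can record such a child, and database recruitment starts from registration at fitting rather than from confirmed use. Two analysts could therefore report different PEACH results from the same data, and the choice could be made after the scores are known.

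Overall PEACH is a primary endpoint. If the device was not worn, the listening items might describe hearing without it, and PEACH item 1 lowers the total for non-wear directly. In a descriptive study, who is being described is the heart of the result, so the question is a fair one.

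**Working it through.** **Step 1: do the sections define two populations?**

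| Place | Term for the child |
|---|---|
| Synopsis | currently using |
| 5.3 | currently wearing |
| 8.1, Objective A | wearing |
| 9.1, opening | use |
| 9.1, on timing of enrolment | fitted |
| 9.1.1, first bullet | user |
| 9.1.1, third bullet | users, fitted |
| 9.2.1, softband questionnaire | currently fitted |

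Use or wear appears in the Synopsis, 5.3, 8.1, 9.1 and 9.1.1. The sentence in 9.1 that mentions fitting concerns when enrolment may happen, not who qualifies. The third bullet of 9.1.1 begins with users and adds that they are fitted at the time of the survey. *User* is nowhere defined, so 9.1.1 neither plainly admits nor plainly excludes a child with zero use. This is loose vocabulary, not two competing standards.

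**Step 2: does a none on item 10 identify a child who is not a wearer?**

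Not by itself. The item covers two weeks, so a temporary break would also produce that answer. Appendix A states no recall period for PEACH, so the PEACH answers need not refer to the same fortnight. It cannot be assumed that PEACH items 3 to 13 describe unaided hearing in such a child.

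**Step 3: what would an analyst do under Section 11?**

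The section summarises questionnaire results and has no exclusion based on use. Dropping an enrolled, eligible respondent would need authority that the text does not give. The default is inclusion.

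**Step 4: how large could the effect be?**

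The plan has no figure to reproduce: the target of 40 is stated not to be hypothesis-driven, and no PEACH scoring rule or expected score is given. For illustration, take n = 40 respondents (9.1.3), k with zero use, and a mean PEACH score d percentage points lower in those children. With W as the wearers' mean:

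mean of all = [(40 − k) × W + k × (W − d)] / 40 = W − k × d / 40

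| k | d = 10 | d = 20 | d = 30 |
|---|---|---|---|
| 1 | 0.25 | 0.50 | 0.75 |
| 4 | 1.0 | 2.0 | 3.0 |
| 8 | 2.0 | 4.0 | 6.0 |

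Both k and d are assumptions. If all 13 items are summed (also an assumption), the maximum is 13 × 4 = 52, and PEACH item 1 alone separates a never-wearer from an always-wearer by 4/52 = 7.7%. That moves the mean by 7.7/40 = 0.19 points per zero-use child, or 0.77 points for four.

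One low value can set the reported minimum, but it hardly affects the median. Removing the lowest of 40 values moves the median from midway between the 20th and 21st values to the 21st, which is half the gap between two neighbouring scores.

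**The case for a change.** The strongest case for a change is that *user* does not settle the matter. Section 9.1 applies the word to a database that families join at fitting, and 9.2 calls the people in that database users, so the word may mean no more than registered. No section says what happens when a parent answers No to item 1 or none to item 10. Under the fitted reading there is no deviation for Section 14 to classify, and Section 14 in any case leaves consequences to the end of the study. The remedy would be cheap: a few sentences and one table from items already collected.

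Part of this stands. The terms do vary, and the handling of zero use is not written down. It does not follow that the plan must change.

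The obvious repair, a wearers-only set as the main PEACH result, is debatable. It can flatter the device. It also sits badly with a call for a single definition: if the definition is wearing, zero-use children are ineligible for GCBI and satisfaction too; if it is fitted, the main PEACH set departs from it.

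The worry about a choice made after seeing the scores is limited by Section 11, whose plain reading keeps everyone. The hours item belongs to a questionnaire that Section 11 already covers, so reporting how many parents answered none is ordinary practice under the plan.

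**Conclusion.** The concern does not call for a change. What remains is missing detail that analysts can fill sensibly: summarise PEACH for all eligible respondents, as Section 11 reads, alongside the item 10 results. That describes enrolled users honestly and does not select the children who do best.

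The size is unknown and may be nil, because the documents give no count of zero-use children. Under the assumed gap of 10 to 30 percentage points, one such child among 40 lowers the mean by 0.25 to 0.75 points and four lower it by 1.0 to 3.0. A shift of several points would need something like eight in 40, or 20% of the sample, and nothing in the documents suggests that number. There is no hypothesis test, so no error rate or power is affected.

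The varying terms, and the absence from 9.1.1 of the under-18 limit given in the Synopsis and 5.3, are matters of drafting. The conclusion rests on reading Section 11 as including every eligible respondent and on *user* in 9.1 and 9.1.1 carrying its ordinary sense.

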9.2 Investigation Procedures

Out-reach will be made through email to registered participants, parents or primary caregivers of children, fitted with a Ponto device on a softband in the US Salesforce database. The participants in the US Salesforce database had previously consented to being contacted by Oticon Medical in the future. The email will be sent through the Salesforce database and contain general information about the study as well as a link to the study landing page, created and hosted in SMART-TRIAL. On the landing page more information about the survey is provided and participants are asked to proceed with sign-up by providing their email address. At this point the participant is assigned a unique identification number. Following providing consent, the participant will be provided with access to the survey in SMART-TRIAL. Periodic reminders, one after one week, another after four weeks, and after five weeks will be sent from SMART-TRIAL if consent has been provided by survey not completed.

Out-reach efforts will also be made through Oticon Medical's social media accounts (such as linked-in, facebook, etc). Additionally, clinics and providers in the US who have active pediatric populations fitted with Ponto sound processors on softband who have expressed interest in assisting recruitment efforts may also be included in reach out efforts. Interested clinics will be provided with a one-page informational flyer to provide to parents of children who meet the inclusion criteria. The flyer will have the same information as the social media postings as well as emails sent to the users in the Salesforce database.

9.2.1 *Surveys*

PEACH

The Parent's Evaluation of Aural/Oral Performance of Children (PEACH) was developed to evaluate the effectiveness of amplification for infants and children with hearing impairment by a systematic use of parents' observations. The PEACH questionnaire is composed of 13 questions that examines a child's auditory performance in quiet and noisy listening conditions and has been shown to have good internal consistency and high test-retest reliability. The PEACH can be used with infants as young as one month old and with school-aged children who have hearing loss ranging from mild to profound degree.

GCBI

The Glasgow Children's Benefit Inventory (GCBI) was designed to retrospectively assess quality of life benefits

after a healthcare intervention. The GCBI is a parent-completed questionnaire comprised of 24 questions that query various aspects of a child's daily life and is worded to apply to children of any age. The GCBI is commonly modified to be used in any area of paediatric medicine. For this study, "operation" will be adapted to "Ponto sound processor on Softband", (Appendix B).

Softband specific questionnaire

The softband-specific questionnaire was developed by Oticon Medical and consists of questions designed to be completed by parents or other caregivers of children who are currently fitted with a Ponto sound processor on a softband.

10 MONITORING

Not applicable.

11 STATISTICAL DESIGN AND ANALYSIS

The results of the questionnaires will be analyzed and presented using descriptive statistics including the mean, standard deviation, median, and range.

The sample size in the investigation is not hypothesis-driven, but rather based on the number of users in the database which fit the inclusion criteria as well as estimations derived from previous survey study response rates from social media and other Oticon Medical reach out efforts.

No imputations or estimations will be made to replace missing data.

12 DATA MANAGEMENT

All data collected and processed concerning the subjects participating in the study are protected under the Regulation (EU) 2016/679 (GDPR) and Health Insurance Portability and Accountability Act (HIPAA) and will be handled accordingly. Further, professional secrecy regarding subject information and data applies to all involved personnel.

The data from the online survey will be recorded into a secure, password protected electronic data capture (EDC) system. Only relevant study personnel will be given a password to access the EDC. A two-factor authentication system will also be in place when logging into the EDC and an automatic logout in place if the user in the EDC has been idle for more than ten minutes.

In the EDC system all subjects enrolled in the study will be assigned a three-digit Subject Identification Number (SIN) with a link to their personal identification (email address), which will not be stored in the EDC, but on a secure, password protected Oticon Medical Server.

The personal identification information will be used for sending out emails with the surveys. The subject can at any time ask to get their personal identification information removed. The access to the EDC system is restricted and will be limited to a couple of users with administrative rights.

13 AMENDMENTS TO THE CIP

Substantial amendments will be approved by the IRB/EC, before incorporated. For non-substantial

amendments, local regulations regarding notifications to IRB/EC will be followed, if applicable.

If the study is to be deemed exempt via IRB/EC approval, non-substantial amendments to this protocol and accompanying material will be made without notifying the IRB/EC. Only on the occurrence wherein amendments to the protocol are made that might affect the exemption, the IRB/EC will be notified.

14 DEVIATIONS FROM CLINICAL INVESTIGATION PLAN

All protocol deviations will be documented stating the reason, date, the action(s) taken, and the impact for the participants/users and/or the study. At the end of the study, protocol deviations will be categorized as minor or major and their consequence on analysis and study conclusions will be determined.

15 DEVICE ACCOUNTABILITY

Not applicable.

16 STATEMENTS OF COMPLIANCE

The CIP, the Subject Information, the Online Informed Consent Form (ICF) and other required documents will be submitted to an IRB/EC Documentation will be reviewed and approved, or deemed exempt, in writing, by IRB/EC before enrolment of subjects into the study can be initiated. Any additional requirements imposed by IRB/EC shall be followed.

17 INFORMED CONSENT PROCESS

Participants will be given full and adequate written information about the nature and purpose of the investigation, including data handling privacy procedures and possible risks involved. Potential participants will also be notified that they are free to decline participation in the investigation, and that they are free to discontinue at any time, without any consequences to their future care. Sufficient time will be given for consideration to participate and the opportunity to ask questions will be provided. Contact details for research personnel who are available to answer any questions will be provided to potential participants. Subject consent will be obtained electronically, documented, and stored in the secure EDC system.

If any new information becomes available during the investigation that possibly could influence the participant's willingness to participate, they will be informed and asked to provide electronic consent for a revised informed consent document, if applicable.

18 ADVERSE EVENTS, ADVERSE DEVICE EFFECTS, AND DEVICE DEFICIENCIES

Adverse events, adverse device effects, and device deficiencies will be covered by normal post-market complaints handling, including unexpected findings from primary and secondary objectives, i.e., participant reported outcomes on the subjective performance and satisfaction of their softband device.

19 SUSPENSION OR EARLY TERMINATION OF THE INVESTIGATION

The sponsor may prematurely terminate the study at any time. If the investigation is suspended or terminated prematurely, any applicable regulatory authorities and ECs/IRBs concerned will be informed promptly in writing.

20 PUBLICATION POLICY

A description of this study will be available, throughout the duration and onwards, on www.ClinicalTrials.gov.

When the study is completed, even if prematurely terminated, a final report will be compiled, and the results will be made publicly available. The results obtained in the study might be submitted for publication in scientific journals by the sponsor. Privacy and confidentiality of information about each subject will be preserved in any reports and any publications of the clinical Study data.

23 APPENDICES

A. PEACH

	Question	Never 0%	Seldom 1 - 25%	Sometimes 26 - 50%	Often 51 - 75%	Always 75-100%
1	How often has your child worn his/her hearing aids and/or cochlear implant?	0	1	2	3	4
2	How often has your child complained or been upset by loud sounds?	4	3	2	1	0
3	When you call, does your child respond to his/her name in a quiet situation?	0	1	2	3	4
4	When asked, does your child follow simple instructions or do a simple task in a quiet situation?	0	1	2	3	4
5	When you call does your child respond to his/her name in a noisy situation when he/she can't see your face? (examples of responses include looks up, turns, answers verbally)	0	1	2	3	4
6	When asked, does your child follow simple instructions or do a simple task in a noisy situation?	0	1	2	3	4
7	When you are in a quiet place reading with your child, how often does he/she pay close attention to what you are saying? OR if your child is listening to stories/songs on the TV or CD when there is no other background noise how often can he/she follow what is being said?	0	1	2	3	4
8	How often does your child initiate/participate in conversation in a quiet situation?	0	1	2	3	4
9	How often does your child initiate/participate in conversation in a noisy situation?	0	1	2	3	4
10.	How often does your child understand what you say in the car/bus/train?	0	1	2	3	4

11.	How often does your child recognize peoples' voices without seeing who was talking?	0	1	2	3	4
12.	How often does your child successfully use a phone?	0	1	2	3	4
13.	How often does your child respond to sounds other than voices?	0	1	2	3	4

B. GCBI questionnaire

1. Has your child's Ponto sound processor on softband made his/her overall life better or worse?						
a) much better b) a little better c) no change d) a little worse e) much worse						
2. Has your child's Ponto sound processor on softband affected the things he/she does?						
a) much better b) a little better c) no change d) a little worse e) much worse						
3. Has your child's Ponto sound processor on softband made his/her behaviour better or worse?						
a) much better b) a little better c) no change d) a little worse e) much worse						
4. Has your child's Ponto sound processor on softband affected his/her progress or development?						
a) much better b) a little better c) no change d) a little worse e) much worse						
5. Has your child's Ponto sound processor on softband affected how lively he/she is during the day?						
a) much better b) a little better c) no change d) a little worse e) much worse						
6. Has your child's Ponto sound processor on softband affected how well he/she sleeps at night?						
a) much better b) a little better c) no change d) a little worse e) much worse						
7. Has your child's Ponto sound processor on softband affected his/her enjoyment of food?						
a) much better b) a little better c) no change d) a little worse e) much worse						
8. Has your child's Ponto sound processor on softband affected how self-conscious						

he/she is with other people?				
a) much better	b) a little better	c) no change	d) a little worse	e) much worse
9. Has your child's Ponto sound processor on softband affected how well he/she gets on with the rest of the family?				
a) much better	b) a little better	c) no change	d) a little worse	e) much worse
10. Has your child's Ponto sound processor on softband affected his/her ability to spend time and have fun with friends?				
a) much better	b) a little better	c) no change	d) a little worse	e) much worse
11. Has your child's Ponto sound processor on softband affected how embarrassed he/she is with other people?				
a) much better	b) a little better	c) no change	d) a little worse	e) much worse
12. Has your child's Ponto sound processor on softband affected how easily distracted he/she has been?				
a) much better	b) a little better	c) no change	d) a little worse	e) much worse
13. Has your child's Ponto sound processor on softband affected his/her learning?				
a) much better	b) a little better	c) no change	d) a little worse	e) much worse
14. Has your child's Ponto sound processor on softband affected the amount of time he/she has had to be off nursery, playgroup or school?				
a) much better	b) a little better	c) no change	d) a little worse	e) much worse
15. Has your child's Ponto sound processor on softband affected his/her ability to concentrate on a task?				
a) much better	b) a little better	c) no change	d) a little worse	e) much worse
16. Has your child's Ponto sound processor on softband affected how frustrated and irritable he/she is?				
a) much better	b) a little better	c) no change	d) a little worse	e) much worse
17. Has your child's Ponto sound processor on softband affected how he/she feels about him/herself?				
a) much better	b) a little better	c) no change	d) a little worse	e) much worse
18. Has your child's Ponto sound processor on softband affected how happy and content he/she is?				

a) much better b) a little better c) no change d) a little worse e) much worse

19. Has your child's Ponto sound processor on softband affected his/her confidence?

a) much better b) a little better c) no change d) a little worse e) much worse

20. Has your child's Ponto sound processor on softband affected his/her ability to care for him/herself as well as you think he/she should, such as washing, dressing, and using the toilet?

a) much better b) a little better c) no change d) a little worse e) much worse

21. Has your child's Ponto sound processor on softband affected his/her ability to enjoy leisure activities such as swimming and sports and general play?

a) much better b) a little better c) no change d) a little worse e) much worse

22. Has your child's Ponto sound processor on softband affected how often he/she needs to visit a doctor?

a) much better b) a little better c) no change d) a little worse e) much worse

23. Has your child's Ponto sound processor on softband affected how prone he/she is to catch colds or infections?

a) much better b) a little better c) no change d) a little worse e) much worse

24. Has your child's Ponto sound processor on softband affected how much medication he/she has needed to take?

a) much better b) a little better c) no change d) a little worse e) much worse

C. Softband specific questionnaire**1. Is your child currently using a Ponto sound processor on a softband?**

Yes

No

2. What is your child's date of birth? (Please use MM/DD/YYYY format)

 /

 /

3. What is your child's gender?

Male

Female

Other

Do not wish to disclose

4. Approximately how long has your child experienced hearing problems?

Less than a year

1 to 3 years

3 to 6 years

6 to 9 years

more than 9 years

I'm not certain

Since birth

5. How long has your child been using a Ponto sound processor on softband?

Less than a year

1 to 3 years

3 to 6 years

6 to 9 years

more than 9 years

I'm not certain

Since birth

6. Is your child using one or two Ponto sound processor(s)?

1 – One sound processor

2 - Two sound processors (one on the left, one on the right)

7. Is your child currently using a Softband 5 or other softband?

Softband 5

Other softband

I'm not sure

8. Is this your child's first softband?

Yes, this is the first

No, they used a different generation softband in the past

I'm not sure

9. Which Ponto sound processor does your child currently use?

Ponto 3

Ponto 3 Power

Ponto 3 SuperPower

Ponto 4

Ponto 5 Mini

Ponto 5 SuperPower

I don't know / other model

10. Think about how much your child used their sound processor(s) over the past two weeks. On an average day, how many hours did they use the sound processor(s)?

none
less than 1 hour a day
1 to 4 hours a day
4 to 8 hours a day
more than 8 hours a day

**11. Think about a situation where your child wanted to hear better, before receiving their sound processor.
Over the past two weeks, how much has the sound processor(s) helped in that situation?**

helped not at all
helped slightly
helped moderately
helped quite a lot
helped very much

12. How satisfied overall are you with your child's Ponto experience?

very much
quite a lot
moderately
slightly
not at all

13. How satisfied overall are you with your child's softband?

very much
quite a lot
moderately
slightly
not at all

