6 JUSTIFICATION FOR THE INVESTIGATION

The study is a non-interventional, observational, study on users of Ponto sound processors who use their sound processors on a softband solution. The purpose of this study is to assess subjective benefit by evaluating performance and overall satisfaction of the Ponto on a Ponto Softband in pediatric users.

This study will utilize responses from survey questions of parents or primary caregivers of children fitted with a softband solution. The survey will collect responses relating to reported hearing improvements and quality of life.

The study will use the PEACH questionnaire¹ to evaluate performance. The PEACH is a measure used by hearing health professionals to evaluate the effectiveness of a child's use of hearing in real-world environments. PEACH is validated with norms scale (English). This study will also use the GCBI questionnaire², modified to specifically query a child's quality of life after receiving their Ponto sound processor on softband. Additionally, a specialized questionnaire is constructed to gather feedback on wear and general comfort of Oticon Medical Softband.

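### PEACH item 1 asks about hearing aids or a cochlear implant, not the Ponto on softband, and the plan records no instruction telling parents which device to answer for

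*Combined protocol and SAP*

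**What the plan says.** The Synopsis lists the overall PEACH score among the primary endpoints, and Section 8.1 ties PEACH to hearing performance with the Ponto on softband. Appendix A prints 13 items, each scored 0 to 4. Item 1 is "How often has your child worn his/her hearing aids and/or cochlear implant", with answers from Never (0) to Always (4) and no not-applicable option.

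The GCBI is treated differently. Section 6 says it is "modified to specifically query a child's quality of life after receiving their Ponto sound processor on softband", and Section 9.2.1 repeats that the study device replaces the reference to an operation. Section 6 describes PEACH as validated with norms. Neither section mentions an adaptation of PEACH or an instruction to go with it.

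For eligibility, Section 9.1.1 requires "Users fitted with at least one Ponto Sound Processor on a softband at the time of the survey". It does not exclude a child who also uses another hearing device. In Appendix C, item 6 asks whether one or two Ponto processors are used and item 9 asks "Which Ponto sound processor does your child currently use". No item asks about a device that is not a Ponto.

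**The concern.** Read literally, item 1 asks about devices other than the one being studied. The plan's own vocabulary encourages that reading: Appendix C calls the Ponto a sound processor, and Sections 4.1 and 5.3 present the softband as an option for people who gain no benefit from conventional hearing aids.

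Three kinds of unintended answer are possible:

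- A parent whose child uses only a Ponto answers Never.
- A parent whose child also has another device answers about that device.
- A parent leaves the item blank. Section 11 rules out imputation, and the plan gives no rule for scoring an incomplete PEACH.

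If item 1 counts in the overall score, a primary-endpoint value then moves for a reason that has nothing to do with the Ponto. A mistaken Never moves it down. An answer about another device that is worn more than the Ponto moves it up. Because Appendix C does not record other devices, the affected children could not be identified afterwards.

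**Working it through.** **Item counts.** Section 9.2.1 states 13 PEACH and 24 GCBI items, and the appendices agree with both figures.

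| Questionnaire | Items | Name the Ponto on softband | Name another hearing device |
|---|---|---|---|
| PEACH (Appendix A) | 13 | 0 | 1 (item 1) |
| GCBI (Appendix B) | 24 | 24 | 0 |

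**Inputs for the size of the effect.** Item scores run from 0 to 4 (Appendix A), there are 13 items, and the planned number is 40 (Section 9.1.3: "The aim is to enroll 40 participants within 24 months"). The plan gives no PEACH scoring rule, so two cases are needed.

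*Case A: item 1 is not scored.* The shift in the overall score is 0. Only the reported wear answer is unclear.

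*Case B (assumption): all 13 items are summed and rescaled to 0–100.* The maximum sum is 13 × 4 = 52.

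Shift for one child = 100 × (category error)/52. Shift in the group mean per wrong answer = that value/40.

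| True Ponto wear | Answer given | One child, points of 100 | Mean of 40, per wrong answer |
|---|---|---|---|
| Always (4) | Never (0) | −4/52 = −7.69 | −0.192 |
| Often (3) | Never (0) | −3/52 = −5.77 | −0.144 |
| Sometimes (2) | Never (0) | −2/52 = −3.85 | −0.096 |
| Seldom (1) | Never (0) | −1/52 = −1.92 | −0.048 |
| Seldom (1) | Always (4), about another device | +3/52 = +5.77 | +0.144 |

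**Wrong answers needed to move the mean by 1 point.** The 1-point mark is a yardstick chosen here; the plan sets none.

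- Never instead of Always: 1/0.192 = 5.2, so 6 of 40 (15%). Check: 5 × 0.192 = 0.96 and 6 × 0.192 = 1.15.
- Never instead of Often: 1/0.144 = 6.9, so 7 of 40 (17.5%).

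**Range over misreading rates.** The documents give no rate. For illustration only, if 10%, 25% or 50% of parents answered Never instead of Always, the mean would fall by 0.10 × 7.69 = 0.8, 0.25 × 7.69 = 1.9 or 0.50 × 7.69 = 3.8 points.

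**The case against.** The strongest reply is that leaving PEACH as published is a reasonable choice. The GCBI had to change because it refers to an operation, which a softband does not involve, and Section 9.2.1 says it is commonly modified. PEACH is presented as validated with norms. The GCBI adaptation does not by itself make the PEACH wording an error. This stands, and it is why the fix leaves the wording alone. If the wording was kept on purpose, though, the plan does not say so.

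Next, misreading is conjecture. Parents are recruited as parents of Ponto softband users, the other two questionnaires name the Ponto throughout, and the eligibility phrase about at least one Ponto most naturally means one or two of them. Many parents will read the item as intended. This stands too, and no rate is claimed. It does not remove the ambiguity, because the printed item names other devices and offers no way to say that it does not apply.

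Third, Appendix C item 10 already collects daily hours of sound-processor use. It does, but nothing in the plan links it to the PEACH score.

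Finally, if some children use a second device, the listening items may reflect both devices together, and an instruction justified for item 1 does not settle that. This is correct. The present point is limited to item 1.

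**Conclusion.** The concern holds and is minor. As printed, a scored item in a primary-endpoint questionnaire asks about devices other than the study device, and the plan records nothing to redirect the parent.

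The effect on the overall score is zero if item 1 is unscored. If all 13 items are summed, it is at most 7.7 points of 100 for one child and 0.19 points on the mean of 40 per wrong answer. Three things are unknown from the documents: the scoring rule, the misreading rate, and whether the survey screen already carries a clarification. Section 11 plans descriptive statistics only, with no test or threshold, so no formal conclusion depends on this item.

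**What to change.** 1. Keep the published wording of item 1 and add an on-screen instruction, for example: *Please answer for the Ponto sound processor on softband, even if your child also uses another hearing device.* Record it in Section 9.2.1, as is done for the GCBI. If such an instruction already exists, only the record is needed.
2. Optionally, for responses already collected, report how many parents answer Never on PEACH item 1 but give one or more hours a day on Appendix C item 10. This is a partial check. Item 10 uses hour bands over the past two weeks, whereas item 1 as printed has no recall period. The check also cannot detect an Always given about another device.
3. As a related request, state in Section 11 whether item 1 counts in the overall PEACH score.

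The cost of the main change is one instruction and one sentence, with no extra question for parents. The downside is a documented clarification to a normed questionnaire, which should be noted in any comparison with the norms. If some responses were collected before the instruction was added, the two sets should be identifiable.
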